2.2 Violations and deviations

Patients who do not meet eligibility criteria but are randomised will be analysed according to the analysis sets described in Section 2.1. There is no intention to perform a per-protocol analysis in BORA.

2.2.1 Important protocol deviations

The important protocol deviations are important in that they may significantly affect the assessments of the study safety outcomes.

The final list of protocol deviations will be reviewed, finalised and documented prior to database lock. Only important protocol deviations will be listed and tabulated in the Clinical Study Report (CSR). The following categories of protocol deviations will be reviewed by medical advisors and statisticians prior to database lock to determine those which are considered important deviations:

- Patients who do not meet the inclusion criteria
- Patients who meet any of the exclusion criteria
- Concomitant use of disallowed medications (to be identified through programming). Patients who use one or more disallowed medication (for any reason, unless otherwise specified) during the treatment period will be classed as protocol deviators
- Patients who received the incorrect study dose regimen
- Patients who developed withdrawal criteria during the study but were not withdrawn

Any patients with anomalies in the plasma concentrations, determined as follows, will be flagged and discussed in the CSR:

- Patients for whom all collected plasma concentration levels are persistently below the LLOQ (3.86 ng/ML) throughout the treatment period
- Patients with plasma concentrations in excess of what is considered to be physiologically possible with dosing (ie concentrations $\geq 12,000$ ng/ML)

A listing will be prepared for these patients highlighting the PK sampling times along with their results from the ADA and eosinophil assessments.

2.3 Adjusted visit window definitions

For the exacerbation-related analyses, no windows will be applied. For local electrocardiogram (ECG), vital signs, Work Productivity and Activity Impairment Questionnaire plus Classroom Impairment Questions (WPAI+CIQ), and post-bronchodilator spirometry, the visit recorded in web-based data capture (WBDC) will be used. For other visit-based data the variables will be summarised based on the collection study days with adjusted visit windows.

The adjusted analysis-defined windows will be based on the collection schedule listed in the protocol, and collected assessments will be windowed to the closest scheduled visit for the variable of interest. Visit windows have been constructed so that every observation collected can be allocated to a particular visit. The adjusted windows are summarised in [Table 2 – Table 8 in Appendix A](#) [Analysis visit windows](#)

For assignment of data to adjusted analysis-defined visit windows, study day is defined as follows:

$$(Date\ of\ assessment - date\ of\ first\ dose) + 1$$

By this definition, the day of first dose will be Study Day 1 and the planned date of Visit 2 (Week 4) will be Study Day 29 (=28+1), for example.

If multiple readings are recorded within a single adjusted visit window, in general, the following rules will be applied:

- If there are 2 or more observations within the same adjusted visit window, then the non-missing one closest to the scheduled study day will be used in the analysis.
- If 2 or more observations are equidistant from the scheduled study day, then the non-missing observation with the earlier collection date will be used in the analysis.
- If 2 or more observations are collected on the same day, then the non-missing one with the earlier collection time will be included in the analysis.

If an adjusted visit window does not contain any observations, then the data will remain missing.

For the overall analyses that are not based on any particular study visit, all data will be listed and/or analysed, including any repeat or unscheduled visits, unless otherwise specified. For example, for safety summaries, all post-baseline results will be included in the overall analysis up to and including the FU visit.

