8. APPENDICES

8.1 Appendix A Analysis visit windows

Table 2 Adjusted visit windows for variables with scheduled visits every 4 weeks (eg, EQ-5D-5L)

| Analysis Visit | Scheduled study day | Adjusted visit window |
|--------------------------|---------------------|----------------------------------|
| Week 0 | 1 | Study Day \leq 1 |
| Week 4 | 29 | 2 \leq Study Days \leq 42 |
| Week 8 | 57 | 43 \leq Study Days \leq 70 |
| Week 12 | 85 | 71 \leq Study Days \leq 98 |
| Week 16 | 113 | 99 \leq Study Days \leq 126 |
| Week 20 | 141 | 127 \leq Study Days \leq 154 |
| Week 24 | 169 | 155 \leq Study Days \leq 182 |
| Week 28 | 197 | 183 \leq Study Days \leq 210 |
| Week 32 | 225 | 211 \leq Study Days \leq 238 |
| Week 36 | 253 | 239 \leq Study Days \leq 266 |
| Week 40 | 281 | 267 \leq Study Days \leq 294 |
| Week 44 | 309 | 295 \leq Study Days \leq 322 |
| Week 48 | 337 | 323 \leq Study Days \leq 350 |
| Week 52 | 365 | 351 \leq Study Days \leq 378 |
| Week 56 (EOT for adults) | 393 | 379 \leq Study Days \leq 406 |
| Week 68# (FU for adults) | 477 | 407 \leq Study Days |
| Week 60* | 421 | 407 \leq Study Days \leq 434 |
| Week 64* | 449 | 435 \leq Study Days \leq 462 |
| Week 68* | 477 | 463 \leq Study Days \leq 490 |
| Week 72* | 505 | 491 \leq Study Days \leq 518 |
| Week 76* | 533 | 519 \leq Study Days \leq 546 |
| Week 80* | 561 | 547 \leq Study Days \leq 574 |
| Week 84* | 589 | 575 \leq Study Days \leq 602 |
| Week 88* | 617 | 603 \leq Study Days \leq 630 |
| Week 92* | 645 | 631 \leq Study Days \leq 658 |
| Week 96* | 673 | 659 \leq Study Days \leq 686 |
| Week 100* | 701 | 687 \leq Study Days \leq 714 |

Table 2 Adjusted visit windows for variables with scheduled visits every 4 weeks (eg, EQ-5D-5L)

| Analysis Visit | Scheduled study day | Adjusted visit window |
|---------------------------------|---------------------|-----------------------|
| Week 104* | 729 | 715≤Study Days≤742 |
| Week 108* (EOT for adolescents) | 757 | 743≤Study Days≤770 |
| Week 120* (FU for adolescents) | 841 | 771≤Study Days |

Visit for adults only.

* Visits for adolescents only.

Table 3 Adjusted visit windows for variables with scheduled every 12 weeks visits (eg, ACQ-6 and AQLQ(S)+12)

| Analysis Visit | Scheduled study day | Adjusted visit window |
|---------------------------------|---------------------|-----------------------|
| Week 0 | 1 | Study Day≤1 |
| Week 12 | 85 | 2≤Study Days≤126 |
| Week 24 | 169 | 127≤Study Days≤210 |
| Week 36 | 253 | 211≤Study Days≤294 |

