| Week 48 | 337 | 295≤Study Days≤378 |
| Week 56# (EOT for adults) | 393 | 379≤Study Days≤434 |
| Week 68# (FU for adults) | 477 | 435≤Study Days |
| Week 60* | 421 | 379≤Study Days≤462 |
| Week 72* | 505 | 463≤Study Days≤546 |
| Week 84* | 589 | 547≤Study Days≤630 |
| Week 96* | 673 | 631≤Study Days≤714 |
| Week 108* (EOT for adolescents) | 757 | 715≤Study Days≤798 |
| Week 120* (FU for adolescents) | 841 | 799≤Study Days |

Visit for adult only.

* Visits for adolescents only.

Table 4a Adjusted visit windows for hematology, cell marker, immunology, microbiology tests

| Analysis Visit | Scheduled study day | Adjusted visit window |
|---------------------------------|---------------------|----------------------------------|
| Week 0 | 1 | Study Day \leq 1 |
| Week 12 | 85 | 2 \leq Study Days \leq 140 |
| Week 28 | 197 | 141 \leq Study Days \leq 252 |
| Week 44 | 309 | 253 \leq Study Days \leq 350 |
| Week 56 (EOT for adults) | 393 | 351 \leq Study Days \leq 462 |
| Week 68# (FU for adults) | 477 | 463 \leq Study Days |
| Week 76* | 533 | 463 \leq Study Days \leq 588 |
| Week 92* | 645 | 589 \leq Study Days \leq 700 |
| Week 108* (EOT for adolescents) | 757 | 701 \leq Study Days \leq 798 |
| Week 120* (FU for adolescents) | 841 | 799 \leq Study Days |

Visit for adult only.

* Visits for adolescents only.

Table 5b Adjusted visit windows for Chemistry laboratory tests - part 1

| Analysis Visit | Scheduled study day | Adjusted visit window |
|---------------------------------|---------------------|----------------------------------|
| Week 0 | 1 | Study Day \leq 1 |
| Week 12 | 85 | 2 \leq Study Days \leq 140 |
| Week 28 | 197 | 141 \leq Study Days \leq 252 |
| Week 44 | 309 | 253 \leq Study Days \leq 350 |
| Week 56 (EOT for adults) | 393 | 351 \leq Study Days |
| Week 56 (For adolescents) | 393 | 351 \leq Study Days \leq 462 |
| Week 76* | 533 | 463 \leq Study Days \leq 588 |
| Week 92* | 645 | 589 \leq Study Days \leq 700 |
| Week 108* (EOT for adolescents) | 757 | 701 \leq Study Days |

Apply for chemistry (excluding tests: Calcium, Chloride, CO₂, Glucose, Phosphorus, Potassium, Sodium, Total cholesterol and Uric acid) and Urine tests.

Visit for adult only.

* Visits for adolescents only.

Table 6c Adjusted visit windows for chemistry laboratory tests - part2

| Analysis Visit | Scheduled study day | Adjusted visit window |
|---------------------------------|----------------------------|----------------------------------|

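### Five Appendix A cut-offs break the SAP's closest-visit rule without explanation, so some late, unscheduled and early-discontinuation assessments get the wrong visit label

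*SAP*

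**What the plan says.** SAP 2.3 gives the allocation rule: "collected assessments will be windowed to the closest scheduled visit for the variable of interest". It counts the day of first dose as Study Day 1, so Week w falls on day 7w + 1. It adds that every observation can be allocated to a visit. When several readings share a window, "then the non-missing one closest to the scheduled study day will be used in the analysis".

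Appendix A (SAP 8.1) then lists the windows. The rows that matter here are:

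- Table 2 (four-weekly variables, with EQ-5D-5L as the example): adult Week 56 (day 393) ends at day 406, and adult follow-up (day 477) is "407 \leq Study Days". Adolescent Week 108 (day 757) ends at day 770, and follow-up (day 841) starts at 771.
- Table 3 (ACQ-6 and AQLQ(S)+12): Week 48 (day 337), a row shared by both age groups, is "295≤Study Days≤378". Adult Week 56 starts at 379.
- Table 4a (haematology and related tests): Week 56, also a shared row, is "351 \leq Study Days \leq 462". Adult follow-up starts at 463.
- Table 8 (pre-bronchodilator spirometry): adolescent Week 96 (day 673) ends at 728, and Week 108 starts at 729.

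Notes under Tables 7 and 8 explain a shortened Week 52 and Week 48 window respectively, both ending at day 385. No note covers the five boundaries above, and 2.3 states no exception.

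**The concern.** The text and the tables are both instructions to the programmer, and at these boundaries they disagree. If the tables are followed, a reading can be filed under a visit that is not its nearest. It may then lose to a better-timed reading in that window, which leaves its proper visit empty.

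The data exposed are by-visit summaries of EQ-5D-5L (the protocol, 8.4.3.4, names the EOT visual analogue score as an outcome), ACQ-6 and AQLQ(S)+12, haematology including eosinophils (a secondary objective through follow-up), and adolescent pre-bronchodilator FEV1.

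The tables also disagree with each other. Adult blood drawn on day 440 is follow-up for ADA under Table 7 (from day 435) but EOT for eosinophils under Table 4a (to day 462).

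**Working it through.** **Inputs.** Scheduled days and windows come from SAP Appendix A, Tables 2 to 8, and the rule from SAP 2.3. Timing after early stopping comes from protocol 3.6: the premature-discontinuation (IPD) visit is 4 weeks, and follow-up 16 weeks, after the last dose, each ±7 days.

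**Formula.** Under a nearest-visit rule the later window starts at (d1 + d2)/2. The tables give the tie day to the later visit: in Table 2, (29 + 57)/2 = 43 and Week 8 starts at day 43.

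**Does this reproduce the tables?** Mostly. I tested all post-baseline boundaries, adults and adolescents separately, counting shared rows once for each group. Of 102, 93 match exactly and 9 do not. Four of the nine are the 385/386 cut-offs in Tables 7 and 8. The other five are:

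| Boundary | Midpoint | Later window starts at | Days given the wrong label |
|---|---|---|---|
| Table 2 adult, Week 56 / follow-up | (393+477)/2 = 435 | 407 | 407-434 (28 days) |
| Table 2 adolescent, Week 108 / follow-up | (757+841)/2 = 799 | 771 | 771-798 (28 days) |
| Table 3 adult, Week 48 / Week 56 | (337+393)/2 = 365 | 379 | 366-378 (13 days) |
| Table 4a adult, Week 56 / follow-up | (393+477)/2 = 435 | 463 | 436-462 (27 days) |
| Table 8 adolescent, Week 96 / Week 108 | (673+757)/2 = 715 | 729 | 716-728 (13 days) |

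Giving the tie day to the earlier visit would move a cut-off by one day, so it explains none of these.

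**Where the adult numbers come from.** They equal adolescent midpoints: (393+421)/2 = 407, (337+421)/2 = 379 and (393+533)/2 = 463. The adult EOT/follow-up boundary, with the same two scheduled days throughout, starts at 407 in Table 2, 435 in Tables 3 and 7, and 463 in Table 4a.

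**Who is touched.** Every day within ±7 of a scheduled day gets the right label in every table. The exposed readings are out-of-window, unscheduled, or timed from an early last dose:

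- An adult EOT EQ-5D-5L on day 410 is 410 − 393 = 17 days from EOT and 477 − 410 = 67 from follow-up, yet is labelled follow-up. If a day-477 value exists, the day-410 value is dropped and EOT is missing.
- An adult last dosed at Week 48 (day 337) has an on-time follow-up at 337 + 112 ± 7 = days 442-456. All 15 days carry the EOT label in Table 4a.
- The same patient's IPD visit falls at 337 + 28 ± 7 = days 358-372. On days 366-372, any ACQ-6 or AQLQ(S)+12 goes to Week 48 under Table 3 although Week 56 is closer, and it loses to a day-337 value.
- An adolescent last dosed at Week 100 (day 701) has an IPD visit at 701 + 28 ± 7 = days 722-736. FEV1 taken on days 722-728 is labelled Week 96.

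**The case against.** **Some cut-offs were chosen on purpose.** The notes to Tables 7 and 8 show this for 385/386. It does not cover the five listed boundaries: Table 3 has the same adult Week 48/56 spacing as Table 8, with no adjustment and no note. Equal half-widths could also explain 407 and 771 (14 days after the scheduled day), 379 (42 days) and 729 (56 days). That would be a different rule from the one 2.3 states, and it does not explain 463.

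**Little depends on it.** This largely stands. Adverse events are classified by the period rules in SAP 3.1.1, and exacerbations are not windowed. ECG, vital signs, WPAI+CIQ and post-bronchodilator spirometry use the recorded visit. Laboratory shift tables use the post-baseline maximum or minimum, and the EQ-5D-5L shift table uses the last observation. The analyses are descriptive.

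**Midpoints have consequences of their own.** This stands too. Under SAP 3.3.1 and 3.3.2 a patient who stopped treatment and has no EOT score is a non-responder. Moving an IPD score from Week 48 to Week 56 supplies an EOT score, so that rule may no longer apply. It is tempting to conclude that the present table turns an observed result into an imputed failure by error. The documents do not go that far: they do not say that an IPD score is meant to serve as EOT, and IPD scores on days 358-364 stay in Week 48 under either cut-off.

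In Table 2, an adult last dosed at Week 44 (day 309) has follow-up at 309 + 112 ± 7 = days 414-428, now labelled follow-up. Midpoints would label it Week 56.

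**Conclusion.** The inconsistency is real: five boundaries depart from the stated rule without explanation and mislabel 13 to 28 days each. The impact is small, confined to late, unscheduled and early-discontinuation assessments in by-visit summaries. The number of patients cannot be derived from the documents.

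Two stronger readings should be resisted. One is that late EOT assessments are generally relabelled as follow-up. That happens only in Table 2; Table 4a errs the other way, and Tables 3 and 8 pull an early EOT or IPD reading back to the preceding visit. The other is that the primary safety results or the exacerbation rates are compromised; neither adverse events nor exacerbations are assigned by these windows.

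Reuse of adolescent cut-offs is an inference from matching arithmetic, and it concerns only the three adult boundaries. The check takes the SAP's own scheduled days as correct. The adult assessment schedule in the protocol is hard to read in the available text, so which assessments are due at the adult IPD and follow-up visits was not confirmed.

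**What to change.** Split the rows now shared by both age groups (Table 2 Week 56, Table 3 Week 48, Table 4a Week 56) and keep the tie day with the later visit:

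- Table 2 adults: Week 56 = 379-434, follow-up from 435.
- Table 2 adolescents: Week 108 = 743-798, follow-up from 799.
- Table 3 adults: Week 48 = 295-364, Week 56 = 365-434.
- Table 4a adults: Week 56 = 351-434, follow-up from 435.
- Table 8 adolescents: Week 96 = 617-714, Week 108 from 715.

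Leave the adolescent Week 48, 56 and 60 windows in Tables 2, 3 and 4a as they are. Editing the shared rows in place would overlap adolescent Week 60 in Table 2 and leave adolescent days 365-378 (Table 3) and 435-462 (Table 4a) unassigned. Table 5b already gives Week 56 separate adult and adolescent rows.

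For 385/386 in Tables 7 and 8, use age-specific midpoints or name them in 2.3 as deliberate exceptions. Any of the five boundaries that was intended can be handled the same way.

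State in 3.3.1 and 3.3.2 whether an IPD score that falls in the EOT window displaces non-responder status, and decide knowingly how to label an early stopper's follow-up EQ-5D-5L.

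The cost is five boundaries (ten windows), three split rows and the matching programming specification. No new data are needed.

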
 1. To assess the impact of 2 dosing regimens of benralizumab on blood eosinophil levels for adult patients during the 56-week treatment period and through the follow-up period (16 weeks from day of last dose) 2. To assess the impact of 2 dosing regimens of benralizumab on blood eosinophil levels for adolescent patients during the 108-week treatment period and through the follow-up period (16 weeks from day of last dose) 	
 • Blood eosinophils

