3.5.2.3 Other restrictions

- (a) Fertile and sexually active patients or their partners should use effective contraceptive methods throughout the study and for at least for 16 weeks (5 half-lives) after last administration of the IP. Male patients should refrain from fathering a child or donating sperm from the time of informed consent and for 16 weeks (5 half-lives) after last dose of IP (see Section 3.1, inclusion criteria 3, 4 and 5; Section 7.3).
- (b) Patients must abstain from donating blood and/or plasma from the time of informed consent and for 16 weeks (5 half-lives) after last dose of IP.

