3.6 Discontinuation from investigational product

Patients will be discontinued from IP in the following situations:

1. Patient decision. The patient is at any time free to discontinue treatment without prejudice to further treatment (see Section 3.7)
2. Adverse event (AE) that in the opinion of the Investigator contraindicates further dosing
3. Risk to patient as judged by the Investigator or AstraZeneca
4. Severe non-compliance to study protocol
5. Eligibility requirement found not to be fulfilled (see Section 3.4)
6. Pregnancy
7. Lost to follow-up³
8. Development of any study specific criteria for discontinuation:
 - (a) Anaphylactic reaction to the IP requiring administration of epinephrine
 - (b) Development of helminth parasitic infestation requiring hospitalization
 - (c) If 2 consecutive doses of IP missed or more than 2 scheduled doses of IP are missed during course of the study

³ Patient is considered lost to follow up when any of the following attempts of contact are failed: -3 attempts of either phone calls, faxes, or emails; - having sent 1 registered letter/certified mail; 1 unsuccessful effort to check the vital status of the patient using publicly available sources, if allowed by local regulations.

(d) An asthma-related event requiring mechanical ventilation

All patients who prematurely discontinue IP should return to the study center and complete the procedures described for the Premature Investigational Product Discontinuation Visit (IPD) within 4 weeks \pm 7 days after the last dose of IP and for the final Follow-up visit at 16 weeks (\pm 7 days) after the last dose of IP (see [Table 1](#) and [Table 2](#)).

Reasons for premature discontinuation of IP should be recorded in the eCRF.

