| Week 0 | 1 | Study Day \leq 1 |
| Week 12 | 85 | 2 \leq Study Days \leq 238 |
| Week 56 (EOT for adults) | 393 | 239 \leq Study Days \leq 574 |
| Week 108* (EOT for adolescents) | 757 | 575 \leq Study Days |

For chemistry labs: Calcium, Chloride, CO₂, Glucose, Phosphorus, Potassium, Sodium, Total cholesterol and Uric acid.

* Visits for adolescents only.

Table 7 Adjusted visit windows for PK (unscheduled samples only) and ADA (including nAb)

| Analysis Visit | Scheduled study day | Adjusted visit window |
|---------------------------------|----------------------------|----------------------------------|
| Week 0 | 1 | Study Day \leq 1 |
| Week 8 | 57 | 2 \leq Study Days \leq 84 |
| Week 16 | 113 | 85 \leq Study Days \leq 154 |
| Week 28 | 197 | 155 \leq Study Days \leq 252 |
| Week 44 | 309 | 253 \leq Study Days \leq 336 |
| Week 52 | 365 | 337 \leq Study Days \leq 385 |
| Week 56# (EOT for adults) | 393 | 386 \leq Study Days \leq 434 |
| Week 68# (FU for adults) | 477 | 435 \leq Study Days |
| Week 60* | 421 | 386 \leq Study Days \leq 476 |
| Week 76* | 533 | 477 \leq Study Days \leq 588 |
| Week 92* | 645 | 589 \leq Study Days \leq 700 |
| Week 108* (EOT for adolescents) | 757 | 701 \leq Study Days \leq 798 |
| Week 120* (FU for adolescents) | 841 | 799 \leq Study Days |

Visit for adult only.

* Visits for adolescents only.

Note that the Week 52 window has a shorter window range (3 weeks) post scheduled study day due to adjustment for adult group having a scheduled EOT visit 4 weeks later.

Table 8 Adjusted visit windows for Pre-BD spirometry

| Analysis Visit | Scheduled study day | Adjusted visit window |
|---------------------------------|---------------------|----------------------------------|
| Week 0 | 1 | Study Day \leq 1 |
| Week 16 | 113 | 2 \leq Study Days \leq 168 |
| Week 32 | 225 | 169 \leq Study Days \leq 280 |
| Week 48 | 337 | 281 \leq Study Days \leq 385 |
| Week 56# (EOT for adults) | 393 | 386 \leq Study Days |
| Week 64* | 449 | 386 \leq Study Days \leq 504 |
| Week 80* | 561 | 505 \leq Study Days \leq 616 |
| Week 96* | 673 | 617 \leq Study Days \leq 728 |
| Week 108* (EOT for adolescents) | 757 | 729 \leq Study Days |

Visit for adult only.

* Visits for adolescents only.

Note that Week 48 window has shorter window range (7 weeks) post scheduled study day due to adjustment for adult group having a scheduled EOT visit 8 weeks later.

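### Adult by-visit windows count only from first dose, so most early stoppers' 16-week follow-up samples are labelled as treatment visits; separately, adult WPAI+CIQ timing differs between protocol and SAP

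*SAP*

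**What the plan says.** SAP 2.3 defines study day from the first dose alone. It says that "collected assessments will be windowed to the closest scheduled visit for the variable of interest" and that "Visit windows have been constructed so that every observation collected can be allocated to a particular visit". Where several values share a window, the one nearest the scheduled day is used. No rule refers to last dose or treatment status. ECG, vital signs, WPAI+CIQ and post-bronchodilator spirometry use the recorded visit, and scheduled PK samples are outside Table 7, so none of these is windowed in this way.

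Protocol 3.6 asks patients who stop early to return for an IPD visit about 4 weeks after the last dose and "for the final Follow-up visit at 16 weeks" (±7 days) after it. The objectives define follow-up on the same clock; the eosinophil objective, for example, covers "blood eosinophil levels for adult patients during the 56-week treatment period and through the follow-up period (16 weeks from day of last dose"). Protocol 3.5.2.3 equates this interval with five half-lives: "16 weeks (5 half-lives) after last administration of the IP".

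SAP 4.1 keeps data collected after discontinuation. SAP 4.1.1 limits adolescents in the adult completion analysis to on-treatment evaluations, and presents adults and adolescents both separately and combined.

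For WPAI+CIQ, protocol 5.3.2.3, 8.4.3.3 and 8.5.1.4 use Visit 1 and EOT. SAP 4.2.7.3 gives baseline and follow-up for adults, and baseline and EOT for adolescents. SAP Section 6 lists no change from the protocol.

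**The concern.** A completer's sample taken 16 weeks after the last dose goes to Week 68 (follow-up). An early stopper's sample at the same interval off drug is usually labelled Week 16, 28, 44 or another treatment visit. Rows that readers will take as describing patients on a regimen then contain values taken five half-lives after the last injection, and the follow-up row represents almost only completers. The summaries at stake are by-visit EQ-5D-5L, haematology, eosinophil change and percent change, and ADA positivity and titre. In the combined adult-adolescent tables of the adult completion analysis, two rules would apply in one row.

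The WPAI+CIQ conflict does not come from the windows. An adult follow-up value with 7-day recall describes a week about 12 weeks after EOT (Week 68 against Week 56), which is not the comparison that the protocol defines.

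**Working it through.** **1. Reproduce the plan's days.** Study day = 7 × week + 1. Week 4 gives 29, Week 56 gives 393 and Week 68 gives 477, as in SAP Appendix A.

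**2. Early stopper's follow-up day.** For last injection at Week L, the day is 7(L + 16) + 1 = 7L + 113. L runs 0, 4, …, 48, which is 13 nominal stop points. L = 12 gives Day 197, exactly Week 28. L = 40 gives Day 393, exactly the adult EOT day.

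**3. Look up the window.**

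| SAP table | Last injection week → label of follow-up sample | Labelled as treatment visit |
|---|---|---|
| Table 2 (EQ-5D-5L) | 0 → Week 16, then in 4-week steps to 40 → Week 56; 44 and 48 → Week 68 | 11 of 13 |
| Table 4a (haematology) | 0 → Week 12; 4-16 → Week 28; 20-32 → Week 44; 36-48 → Week 56 | 13 of 13 |
| Table 7 (ADA) | 0-4 → Week 16; 8-16 → Week 28; 20-28 → Week 44; 32-36 → Week 52; 40-44 → Week 56; 48 → Week 68 | 12 of 13 |

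Moving follow-up by up to 7 days either way leaves 11, 13 and 12 unchanged. Boundary cases only move from one treatment window to another.

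**4. Which value is analysed if an IPD sample also exists** (nominal IPD day 7L + 29).
- Table 4a, nominal days: IPD and follow-up share a window at L = 0, 16 and 32, where follow-up is 28 days from target and IPD 56, so the off-drug value is used. At L = 48, IPD (Day 365) is 28 days away and follow-up (Day 449) is 56, so IPD is used. This leaves 12 of 13.
- Tables 2 and 7, nominal days: no shared window, so 11 and 12 remain. A late follow-up gives the same three counts.
- Follow-up 1-7 days early: in Table 4a, IPD also wins at L = 4 and 20 (28 days against 49-55), leaving 10. In Table 7 the two visits share a window at L = 20, where IPD wins, and at L = 32, where follow-up wins, leaving 11. Table 2 stays at 11.

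**5. Window edges.** The Week 56/68 midpoint is (393 + 477)/2 = 435, which Tables 3 and 7 use. Table 2 starts adult follow-up at Day 407 = (393 + 421)/2, the midpoint to Week 60. Table 4a starts it at Day 463 = (393 + 533)/2, the midpoint to Week 76. Weeks 60 and 76 are adolescent-only visits, so both edges break the closest-visit rule for adults. Moving them to Day 435 alone changes Table 4a from 13 to 12 and Table 2 from 11 to 12, so it does not cure the main problem.

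**6. Size.** The documents give no stopping rate, follow-up attendance or off-drug change. Assume that 10% of adults stop, evenly over the 13 points, and that all attend follow-up. The off-drug share of the Week 28 haematology row is (0.10 × 4/13) / (0.90 + 0.10 × k/13), where k is the number of stop points that supply a Week 28 value. With k = 10 (no IPD sample) it is 0.0308/0.9769 = 3.15%. With k = 12 (IPD sample) it is 0.0308/0.9923 = 3.10%. By the same method:
- haematology: 0.8% at Week 12, 3.2-3.3% at Week 44, 2.5-3.3% at Week 56
- ADA: 1.5-2.5% at Weeks 16-56
- EQ-5D-5L: 0.8-0.9% at each of Weeks 16-56

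The Week 28 haematology figure ranges from 0.8% (5% stop, half attend) to 4.8% (15% stop, all attend).

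**The case against.** Windowing by time since first dose is a declared convention. SAP 4.1 deliberately keeps post-discontinuation data, and the SAP amendment history says that the windows follow the pivotal studies' rules. The study is descriptive and tests no hypothesis, and the planned eosinophil plots use medians, which a few off-drug values hardly move. All of this stands, and it limits the weight of the point. It does not settle the label: keeping a sample is a different decision from calling a follow-up visit Week 28.

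A reader might go further and want Weeks 4-56 limited to the on-treatment period of SAP 3.1.1. The documents do not support that. A completer with last dose on Day 365 and EOT on Day 401 is one day past the cap (365 + 28 + 7 = 400). That value would be barred from Week 56, is not a follow-up visit, and precedes Day 435, so it would have no row. Late IPD samples, and unscheduled samples between IPD and follow-up, could be lost in the same way. Protocol 8.4.1, which sets efficacy over the treatment period, is also only partial support. It covers EQ-5D-5L, and eosinophils only because SAP 4.2.6.3 lists them under efficacy (protocol 8.5.1 does not). It does not cover ADA or other haematology.

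Adult haematology sampling at follow-up and IPD cannot be read from protocol Table 1 in the available text. Follow-up sampling is inferred from the adult follow-up row in SAP Table 4a, titled "Adjusted visit windows for hematology, cell marker, immunology, microbiology tests", and from the eosinophil objective. Sampling at IPD is less certain, so results are shown with and without it.

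**Conclusion.** The mislabelling is real and follows from the SAP's own windows: 11, 13 and 12 of 13 nominal stop points by label. The counts of values actually analysed, when an IPD sample exists, are 11, 12 and 12 at nominal days or with follow-up late, and 11, 10 and 11 with follow-up 1-7 days early. The Week 12 label arises for haematology only; EQ-5D-5L and ADA start at Week 16. The effect is probably small, about 1-3% of values at an assumed 10% stopping with full attendance, and the change off drug is unknown.

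A reader might infer that the safety conclusions are compromised. They are not: AEs, exacerbations, shift tables over the whole post-baseline period, patient-level ADA categories and scheduled PK do not depend on these windows. A reader might also infer that adult WPAI+CIQ was collected at the wrong visit. The documents show an undeclared conflict, but the adult schedule row is unreadable in the available text, so which passage is in error cannot be settled here.

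**What to change.** In SAP 2.3, assign any sample recorded at the 16-week follow-up visit to the follow-up analysis visit, for completers and early stoppers alike, whatever its study day, and remove it from the Week 4-56 windows. Leave every other sample (EOT, IPD including late ones, unscheduled) in the existing windows, so that none loses its row. Set the adult Week 56/68 edge to Day 435 in Tables 2 and 4a, with a separate adult Week 56 row where adolescents now share it.

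The cost is SAP wording and programming; visit labels are already recorded. The treatment rows shrink slightly. Under the 10% assumption, haematology loses 2.3% (IPD sample exists) to 3.1% (none) at Week 28, 2.4-3.3% at Week 44, 2.5-3.3% at Week 56 and 0-0.8% at Week 12. Unscheduled off-drug samples would still sit in treatment rows, which is the price of keeping every sample.

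For WPAI+CIQ, reconcile protocol 5.3.2.3, 8.4.3.3 and 8.5.1.4 and the adult schedule table with SAP 4.2.7.3. If adult EOT data were collected, analyse them. If not, label the adult result as follow-up, 16 weeks after last dose, and declare the change in SAP Section 6.
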